## **AIM 2. Feasibility study of Peer plus**

Knowledge gained from the usability study will be used to revise the Peers plus intervention manual and we will conduct a feasibility study with 20 ethnic minority, community-dwelling older adults with depression. In this study, recruitment, and enrollment procedures as well as eligibility criteria will be identical to the usability study in Aim 1. For the feasibility study, the duration of the Peers plus intervention will be 8 weeks with identical intervention content and process. Data collection procedures will consist of assessment at baseline assessment, post-study assessment and a 3 month follow-up. We will conduct a post-study semi-structured interview.

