## **Data collection**

### Quantitative data

Listed in Table 3 is the timeline of study measures for the usability and feasibility studies. Data obtained from participants recruited for this protocol will include sociodemographic information (e.g., age, race, ethnicity, etc.), attitudes toward technology and technology use, self-reported clinical information (past history of depression services, current mental health service use), self-reported psychosocial measures (physical, social and emotional function, depression, self-efficacy, coping and loneliness) and social determinants of health. We will measure engagement defined in two ways: 1) as attendance of 80% of meetings as reported by peer mentors  and 2) score on the Working Alliance Inventory-SR.

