**Statistical Analysis**

Baseline characteristics, working alliance scores, and clinical and social outcomes were summarized. The Shapiro-Wilk test was applied to check the normality of each outcome measure. Paired-sample t-tests and Wilcoxon signed-rank test were conducted to assess the differences in outcome measures between baseline and post-study, as well as baseline and three-month follow-up scores, to determine statistical significance. For all analyses, a significance level of  $\alpha = 0.05$  was used for two-sided tests unless otherwise specified.

To assess the change in the primary outcome, depressive symptoms over time within the intervention group, a multilevel linear regression model was employed. This model included fixed effects for time points (e.g., baseline, post-intervention, and follow-ups) and covariates such as baseline loneliness, self-efficacy, working alliance scores, and demographic variables that might influence the intervention effects. Random intercepts and slopes were included to account for the repeated measures within participants, allowing for individual variability in both baseline levels and the trajectories of depressive symptoms over time. Additionally, random effects were specified at the peer coach level to account for the nested structure of the data, where participants were grouped by peer coaches. These analyses and data visualizations were conducted using R Statistical Software (v4.2.1; R Core Team 2022).

PHQ\_9

Model	Timepoint	Estimate	Std. Error	95% CI	p-Value	Effect Size(standardized coefficients)	Marginal R^2
Model 1: Basic	Baseline vs Poststudy	-1.93	0.79	(-3.513, -0.344)	0.018	-0.36	0.049
	Baseline vs 3-mons follow-up	-2.88	0.83	(-4.557, -1.209)	0.001	-0.54	
Model 2: Adjusted for demographics #	Baseline vs Poststudy	-1.93	0.79	(-3.509, -0.348)	0.018	-0.36	0.159
	Baseline vs 3-mons follow-up	-2.81	0.83	(-4.488, -1.137)	0.001	-0.53	
Model 3: Full Model ##	Baseline vs Poststudy	-1.78	0.77	(-3.336, -0.230)	0.025	-0.33	0.276
	Baseline vs 3-mons follow-up	-2.42	0.81	(-4.057, -0.784)	0.005	-0.45	

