# Model 2 adjusted for age, gender, education, marital status, race, and employment status.

## Model 3 adjusted for demographic variables and loneliness.

Self-Efficacy

Model	Timepoint	Estimate	Std. Error	95% CI	p-Value	Effect Size(standardized coefficients)	Marginal R^2
Model 1: Basic	Baseline vs Poststudy	2.030	0.824	(0.375, 3.686)	0.017	0.40	0.051
	Baseline vs 3-mons follow-up	2.773	0.870	(1.024, 4.521)	0.003	0.55	
Model 2: Adjusted for demographics #	Baseline vs Poststudy	2.018	0.823	(0.363, 3.673)	0.018	0.40	0.383

	Baseline vs 3-mons follow-up	2.773	0.872	(1.021, 4.525)	0.003	0.55	
Model 3: Full	Baseline vs Poststudy	1.823	0.760	(0.295, 3.351)	0.020	0.48	0.566
	Baseline vs 3-mons follow-up	2.318	0.799	(0.711, 3.926)	0.006	0.55	

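### The SAP names baseline loneliness as a covariate, but the printed Model 3 cannot be a baseline-loneliness main-effect model fitted to Model 2's rows

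*SAP*

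**What the plan says.** The SAP's Statistical Analysis section describes a multilevel linear model for depressive symptoms with time as a fixed effect and "covariates such as baseline loneliness, self-efficacy, working alliance scores, and demographic variables that might influence the intervention effects". The only loneliness score it names is the baseline one. At participant level, "Random intercepts and slopes were included to account for the repeated measures within participants". In addition, "random effects were specified at the peer coach level to account for the nested structure of the data", with no statement of whether these are intercepts or slopes.

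The outcome tables show three nested models. The footnotes state "Model 2 adjusted for age, gender, education, marital status, race, and employment status" and "Model 3 adjusted for demographic variables and loneliness". Model 3 thus differs from Model 2 by loneliness alone. Neither the timing of that score nor the way it entered is given, and no table prints participants or rows per model.

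The Protocol lists loneliness among the "self-reported psychosocial measures (physical, social and emotional function, depression, self-efficacy, coping and loneliness") and, for Aim 2, says "Data collection procedures will consist of assessment at baseline assessment, post-study assessment and a 3 month follow-up". Loneliness scores after baseline may therefore exist.

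**The concern.** The tables contain their own control. In three of the four outcomes, six person-level demographics raise the marginal R² a good deal (PHQ-9 0.049 to 0.159, emotional well-being 0.057 to 0.215, social function 0.068 to 0.304) and leave the post-study contrast where it was. One further covariate, described in the text as a baseline score, then moves all three.

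What is at stake is the meaning of the full model. If loneliness at each visit was entered, and loneliness changed with the intervention (it fell from 36.7 to 31.4 in the pilot under Preliminary studies in the Protocol), Model 3 takes out part of the change it appears to estimate. If rows were lost, it describes a different set of participants or visits. If a loneliness-by-time term was fitted, the printed time effect applies at one unstated loneliness value.

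**Working it through.** **1. Reproduce the printed contrasts.** Midpoint = (lower limit + upper limit)/2, from the baseline-to-post-study confidence intervals in the SAP tables.

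| Outcome | Model 1 | Model 2 | Model 3 | Shift 1 to 2 | Shift 2 to 3 |
|---|---|---|---|---|---|
| PHQ-9 | (-3.513 - 0.344)/2 = -1.9285 | (-3.509 - 0.348)/2 = -1.9285 | (-3.336 - 0.230)/2 = -1.783 | 0.0000 | +0.1455 (7.5% smaller) |
| Emotional well-being | (1.208 + 11.935)/2 = 6.5715 | (1.220 + 11.923)/2 = 6.5715 | (0.159 + 10.591)/2 = 5.375 | 0.0000 | -1.1965 (18.2% smaller) |
| Social function | (-3.557 + 15.164)/2 = 5.8035 | (-3.539 + 15.146)/2 = 5.8035 | (-3.350 + 15.202)/2 = 5.926 | 0.0000 | +0.1225 (2.1% larger) |

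Self-efficacy also moves (2.018 to 1.823, 9.7% smaller). It stays outside the argument because the demographics already shift it slightly (2.030 to 2.018).

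**2. Are the pairs complete?** The fixed values equal simple mean paired differences on 28 pairs: -54/28 = -1.929, 184/28 = 6.571, 162.5/28 = 5.804. The number 28 is inferred, not printed. The zero shifts agree with it. In simulation, one added participant with baseline only let six demographics leave the contrast within 0.0005 in just 1–2% of runs.

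**3. Why a person-constant main effect cannot move the contrast.** Let d be a participant's post-study minus baseline difference. Its mean is the time effect; any time-constant covariate cancels. Remove from the participant's other observations their regression on d. What remains is uncorrelated with d and keeps its own free intercepts, so it carries no information on the time effect. The GLS estimate is then the mean of d, whatever main-effect covariates are added. This holds for any covariance common to participants, including random slopes. A coach intercept also cancels from d. Missing 3-month visits do no harm.

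Numerical check, with assumed PHQ-9-like variances, 28/28/23 visits and 300 runs per setting: adding baseline loneliness moved the contrast by at most about 2 × 10⁻¹⁵ with participant intercepts and slopes plus a coach intercept.

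**4. Where the identity is not exact.** A coach-level random slope, which the SAP does not rule out, breaks it. With complete pairs, the largest loneliness shift in simulation was then about 0.02 to 0.08, depending on the assumed variances, against 0.1455 printed for PHQ-9. With incomplete pairs (32/28/23 visits) it reached 0.29. In both cases the demographics moved the contrast too (medians 0.009 to 0.045). A demographic shift near zero together with a loneliness shift of 0.14 or more occurred in at most 0.3% of runs in any setting.

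**5. What could produce the printed figures.** In 200 REML runs each, the post-study shift was at least 0.146 in these shares of runs:
- visit-level loneliness, assumed to fall by 0.3 SD: 96%
- follow-up rows of two participants dropped: 53%
- baseline loneliness by time, centred 0.3 SD away from the sample mean: 89%
- the same interaction centred at the mean: 0%

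These shares show what is possible, not what is likely. The df implied by half-width/SE fall from about 49 to about 47 for emotional well-being, which fits either an added within-person term or a few lost rows.

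**6. 3-month contrasts.** From Model 2 to Model 3 they shrink by 13.9% (PHQ-9, -2.8125 to -2.4205), 9.5% (emotional well-being), 10.5% (social function) and 16.4% (self-efficacy). These describe the change in the results but prove nothing: not everyone need have a 3-month visit, and demographics already move some of these contrasts (PHQ-9 -2.88 to -2.81).

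**The case against.** The covariate list is introduced as examples, and two of its members, self-efficacy and working alliance, are in no footnote. On that reading the SAP never promises that Model 3 uses baseline loneliness, and the defect is only an undefined covariate. The undefined covariate is real. But the text names no other loneliness score, and the printed figures do not fit the one it names.

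The identity is not absolute, because a coach slope would break it. This weakens social function most: its shift is 0.1225/4.648 = 0.026 of a standard error, against 0.1455/0.79 = 0.18 for PHQ-9 and 1.1965/2.663 = 0.45 for emotional well-being. Judged on size alone, social function could be a coach-slope effect; it counts because its Model 1-to-2 shift is zero. It also moves upward, so it gives no support to the idea that Model 3 removes part of the change.

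The explanations are not all equal. If participants without a baseline score had been dropped whole, Model 3 would again be a paired mean on fewer pairs. With assumed score steps of 1, 4 and 12.5, and n from 15 to 40, -1.783 fits only n = 23, 5.375 only n = 32, and 5.926 none. Loss of whole participants therefore fits poorly. Loss of single visits, visit-level scores and an interaction stay open.

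Finally, this is a single-arm pilot with a preliminary analysis, and a refit must return Model 2's post-study contrasts. That limits the consequence. It does not make the printed figures agree with the text.

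**Conclusion.** The concern holds. The printed Model 3 is not a model with baseline loneliness as a main effect on the rows used for Model 2. The argument is exact for complete pairs with participant-level random effects and a coach intercept. If there is a coach slope or an incomplete pair it is very strong rather than exact, and it is strongest for PHQ-9 and emotional well-being. It rests on the inferred 28 complete pairs; the simulations rest on assumed variances and visit counts.

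The post-study discrepancy is 0.146 PHQ-9 points (7.5%), 1.196 points of emotional well-being (18.2%, p from 0.017 to 0.044) and 0.122 points of social function (2.1%, upward). No conclusion at the 0.05 level changes, and Models 1 and 2 remain valid descriptions of total before-after change. Which alternative was fitted cannot be settled from the documents.

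**What to change.** - Check the code for which loneliness score entered Model 3, in what form, and on which rows.
- Refit Model 3 with the baseline score as a main effect on the rows of Models 1 and 2, and replace the printed figures. If a baseline score is missing for anyone, say so and state how it was handled.
- Print participants and rows for every model.
- If a visit-level or interaction model is kept, show it separately, state its form (and the centring, for an interaction) and label it exploratory; call it mediator-adjusted if it uses visit-level scores.
- Rely on Models 1 and 2 for total change.
- State the timing of loneliness in the footnotes, and make the covariate list in Statistical Analysis match the models shown.

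The cost is a few words in the SAP and one re-run on data already collected. The refitted time effects will look almost the same as Model 2, which is what a baseline covariate should do here.

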# Model 2 adjusted for age, gender, education, marital status, race, and employment status.

## Model 3 adjusted for demographic variables and loneliness.

Self-Efficacy

Model	Timepoint	Estimate	Std. Error	95% CI	p-Value	Effect Size(standardized coefficients)	Marginal R^2
Model 1: Basic	Baseline vs Poststudy	2.030	0.824	(0.375, 3.686)	0.017	0.40	0.051
	Baseline vs 3-mons follow-up	2.773	0.870	(1.024, 4.521)	0.003	0.55	
Model 2: Adjusted for demographics #	Baseline vs Poststudy	2.018	0.823	(0.363, 3.673)	0.018	0.40	0.383

	Baseline vs 3-mons follow-up	2.773	0.872	(1.021, 4.525)	0.003	0.55	
Model 3: Full	Baseline vs Poststudy	1.823	0.760	(0.295, 3.351)	0.020	0.48	0.566
	Baseline vs 3-mons follow-up	2.318	0.799	(0.711, 3.926)	0.006	0.55	

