**Study:**

Feasibility pilot study with approximately 32 participants  
Preliminary analysis of primary (PHQ-9) and secondary outcomes.

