# Model 2 adjusted for age, gender, education, marital status, race, and employment status.

## Model 3 adjusted for demographic variables and loneliness.

#### Emotional Well-being

Model	Timepoint	Estimate	Std. Error	95% CI	p-Value	Effect Size(standardized coefficients)	Marginal R^2
Model 1: Basic	Baseline vs Poststudy	6.571	2.668	(1.208, 11.935)	0.017	0.32	0.057
	Baseline vs 3-mons follow-up	12.566	2.869	(6.801, 18.330)	0.000	0.61	
Model 2: Adjusted for demographics #	Baseline vs Poststudy	6.571	2.663	(1.220, 11.923)	0.017	0.32	0.215
	Baseline vs 3-mons follow-up	12.293	2.870	(6.526, 18.060)	0.000	0.60	
Model 3: Full	Baseline vs Poststudy	5.375	2.593	(0.159, 10.591)	0.044	0.26	0.289
	Baseline vs 3-mons follow-up	11.119	2.784	(5.519, 16.720)	0.000	0.54	

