# Model 2 adjusted for age, gender, education, marital status, race, and employment status.

## Model 3 adjusted for demographic variables and loneliness.

#### Social Function

Model	Timepoint	Estimate	Std. Error	95% CI	p-Value	Effect Size(standardized coefficients)	Marginal R^2
Model 1: Basic	Baseline vs Poststudy	5.804	4.656	(-3.557, 15.164)	0.219	0.20	0.068

	Baseline vs 3-mons follow-up	18.775	4.994	(8.740, 28.809)	0.001	0.65	
Model 2: Adjusted for demographics #	Baseline vs Poststudy	5.804	4.648	(- 3.539, 15.146)	0.218	0.20	0.304
	Baseline vs 3-mons follow-up	18.385	5.004	(8.329, 28.441)	0.001	0.64	
Model 3: Full Model ##	Baseline vs Poststudy	5.926	4.612	(- 3.350, 15.202)	0.205	0.21	0.385
	Baseline vs 3-mons follow-up	16.447	4.944	(6.504, 26.390)	0.002	0.57	

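### Self-efficacy table, Model 3: the effect sizes 0.48 and 0.55 do not follow from the estimates 1.823 and 2.318 on any one SD, nor on the scale of Models 1 and 2

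*SAP*

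**What the plan says.** The SAP (Statistical Analysis) reports four outcome tables: PHQ-9, self-efficacy, emotional well-being and social function. Each has an unadjusted model (Model 1), a model adjusted for demographics (Model 2) and a full model that adds loneliness (Model 3). Each row gives the estimate, SE, 95% CI, p-value and an effect size described as a standardized coefficient. Marginal R² appears once per model. The SAP gives no formula or SD for the standardization.

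The relevant rows of the Self-Efficacy table are:

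- Model 1, post-study: "2.030 0.824 (0.375, 3.686) 0.017 0.40 0.051"
- Model 1, 3 months: "2.773 0.870 (1.024, 4.521) 0.003 0.55"
- Model 3, post-study: "1.823 0.760 (0.295, 3.351) 0.020 0.48 0.566"
- Model 3, 3 months: "2.318 0.799 (0.711, 3.926) 0.006 0.55"

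Model 2 is almost identical to Model 1: estimates 2.018 and 2.773, effect sizes 0.40 and 0.55.

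**The concern.** From Model 1 to Model 3 the post-study estimate falls from 2.030 to 1.823, yet its effect size rises from 0.40 to 0.48. The 3-month estimate falls from 2.773 to 2.318, yet its effect size stays at 0.55. Standardizing divides by a constant, so an effect size should shrink when its estimate does, unless the constant has changed. A changed constant would still have to serve both Model 3 rows.

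What is at stake is how the column reads. Someone comparing models by effect size would conclude that adding loneliness leaves the self-efficacy change as large as before, or larger. The estimates in the same rows say that it gets smaller. Standardized effects are also the figures most easily carried from a pilot into later planning or into comparisons across outcomes.

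**Working it through.** **Inputs.** All 24 rows of the four SAP tables. Estimates are taken as CI midpoints, because the PHQ-9 estimates are printed to only two decimals. Each effect size is allowed ±0.005 for rounding.

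**Step 1: ratio check, which needs no SD.** If effect size = estimate/SD with one SD per model, then (post-study effect size)/(3-month effect size) = (post-study estimate)/(3-month estimate). For self-efficacy Model 3:

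- Estimates: 1.823/2.3185 = 0.786.
- Effect sizes: 0.48/0.55 = 0.873, with rounding limits 0.475/0.555 = 0.856 and 0.485/0.545 = 0.890.

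Estimate ratio against the effect-size range for all 12 pairs:

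| Outcome | Model 1 | Model 2 | Model 3 |
|---|---|---|---|
| PHQ-9 | 0.669 in 0.651–0.682 | 0.686 in 0.664–0.695 | 0.737 in 0.714–0.753 |
| Self-efficacy | 0.732 in 0.712–0.743 | 0.728 in 0.712–0.743 | **0.786 not in 0.856–0.890** |
| Emotional well-being | 0.523 in 0.512–0.537 | 0.535 in 0.521–0.546 | 0.483 in 0.468–0.495 |
| Social function | 0.309 in 0.298–0.318 | 0.316 in 0.302–0.323 | 0.360 in 0.357–0.381 |

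Eleven pairs agree and one does not.

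**Step 2: implied SD = estimate/effect size, self-efficacy.**

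| Row | Post-study | 3 months |
|---|---|---|
| Model 1 | 5.014–5.141 | 4.995–5.087 |
| Model 2 | 4.983–5.109 | 4.996–5.088 |
| Model 3 | 1.823/0.485 to 1.823/0.475 = 3.759–3.838 | 2.3185/0.555 to 2.3185/0.545 = 4.177–4.254 |

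One SD of 5.014–5.087 reproduces all four Model 1 and 2 effect sizes. The two Model 3 ranges overlap neither that range nor each other.

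**Step 3: the other tables as controls.** One SD fits all six rows of each: PHQ-9 5.32–5.36, emotional well-being 20.43–20.66, social function 28.66–28.91. The post-study Model 3 row for emotional well-being, "5.375 2.593 (0.159, 10.591) 0.044 0.26 0.289", implies 5.375/0.265 to 5.375/0.255 = 20.28–21.08, which contains its table's range. The 3-month Model 3 row for social function, "16.447 4.944 (6.504, 26.390) 0.002 0.57", implies 16.447/0.575 to 16.447/0.565 = 28.60–29.11, which does too. Adding loneliness therefore did not change the scale in any other table.

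**Step 4: which column is out of line.** The remaining Model 3 self-efficacy figures agree with one another:

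- CI midpoints are 1.823 and 2.3185, matching the printed estimates.
- CI half-width/SE is 1.528/0.760 = 2.01 and 1.6075/0.799 = 2.01, as in Models 1 and 2.
- t = 1.823/0.760 = 2.40 and 2.318/0.799 = 2.90. On about 48 degrees of freedom (assumed, consistent with the CI width) p is about 0.020 and 0.006, as printed.

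**Step 5: candidate values.**

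- Model 1–2 SD applies: 1.823/5.087 to 1.823/5.014 = 0.358–0.364, and 2.3185/5.087 to 2.3185/5.014 = 0.456–0.462. The printed 0.48 would be 32–34% too high and the printed 0.55 would be 19–21% too high.
- 0.48 is right: the 3-month value would be 2.3185/3.838 to 2.3185/3.759 = 0.60–0.62.
- 0.55 is right: the post-study value would be 1.823/4.254 to 1.823/4.177 = 0.43–0.44.

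**Fall in estimates, Model 1 to Model 3:** (2.030 − 1.823)/2.030 = 10.2% and (2.773 − 2.318)/2.773 = 16.4%.

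**The case against.** The strongest reply is that the SAP never defines the standardization, so a common divisor is an inference and another formula might give 0.48 and 0.55. Three alternatives were tried:

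- **A smaller Model 3 sample** (for example, missing loneliness scores) could change the SD, but the new SD would still apply to both rows. It cannot be about 3.80 for one and 4.22 for the other.
- **Scaling by the SD of each time-point indicator** needs a relative factor of (0.48/1.823)/(0.55/2.318) = 1.11 in Model 3 against (0.40/2.030)/(0.55/2.773) = 0.99 in Model 1. That would require a marked change in who was observed when. The ratio of post-study to 3-month SEs hardly moves: 0.947, 0.944 and 0.951 in Models 1, 2 and 3.
- **t/√n** needs n of about 25 for 0.48 and about 28 for 0.55. No n from 20 to 32 reproduces the Model 1 and 2 values.

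A second reply is that the agreement among estimate, SE, CI and p-value shows only that they came from one model run. The effect sizes could belong to a different Model 3 fit. Strictly, that cannot be excluded, but nothing in the documents suggests it.

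A third reply is that the matter is small. Self-efficacy is secondary in what the SAP calls a "Preliminary analysis of primary (PHQ-9) and secondary outcomes", the estimates stand in the same rows, and no decision rule uses these cells. That is fair and limits the weight of the point, but two reported results remain inconsistent with the figures beside them.

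**Conclusion.** The concern holds. If an effect size is an estimate divided by one outcome SD per model, as the other 22 rows of the four tables indicate, the two Model 3 self-efficacy cells are incompatible with each other. Neither is on the scale of Models 1 and 2. Rounding does not explain the gap. The internal checks place the fault in the effect-size column.

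The values 0.36 and 0.46 rest on the further assumption that Model 3 uses the Model 1–2 SD. That is the likeliest reading, because each other table keeps one SD across its three models. Either of the other repairs would need a separate Model 3 SD for this outcome alone. The documents do not settle which applies. The 0.55 may have been carried over from Models 1 and 2, but this cannot be confirmed either.

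The error does not reach the evidence of change in self-efficacy, which rests on the estimates, CIs and p-values. What is wrong is the apparent effect of adjustment on the size of that change.

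**What to change.** Recompute both Model 3 self-efficacy effect sizes from the model output, using the SD that standardizes Models 1 and 2, and correct the table. State the standardizing SD under each table so that a reader can reproduce the column. If Model 3 was deliberately scaled differently, say so, give the SD, and apply it to both rows.

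The cost is one rerun of the standardization step, one or two corrected cells and a footnote. If the Model 1–2 SD applies, both effect sizes become smaller. No test result changes.
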